8.2 Agent Ordering

A drug supply request form will be supplied to the Investigational Drug Pharmacy.

9.0 Correlative/Special Studies

9.1 Laboratory Correlative Studies

Analysis of pre-metastatic niche density will take place through previously reported techniques. Briefly, a total of 12 4 μ m sections of benign lymph node tissue (derived from paraffin-embedded sections) will be stained with monoclonal antibodies directed at VEGFR1 (ImClone Systems). VEGFR1 clustering will be counted within 8 distinct 40x fields, and the cluster count will be averaged.

Analysis of pSTAT3 and related mediators will be conducted through previously reported techniques. Briefly, 4 mm sections of tumor tissue (derived from paraffin-embedded sections) will be stained with monoclonal antibodies directed at IL-6R (Calbiochem) and pSTAT3 (Santa Cruz Biotechnology). Using both IPLAB and Adobe Photoshop 7.0, random x100 objective fields will be analyzed by selected a standardized color range for immunohistochemical staining. After boundary delineation, the area under the pixilation histogram will be calculated, and the total staining area will be compared to the area of total tissue.

Of note, the laboratory investigator ([name], [name], or associates) will be blinded to the patient randomization. A total of 12 unstained slides derived from tumor and 12 unstained slides derived from normal lymph node tissue will be requested. These slides will be marked with a unique patient identifier number (UPIN) designated by the pathology core facility. Only the study PI and biostatistician will have access to the data to correlate UPIN with patient identification; this data will be housed in a password-protected electronic database.

Blood (a total of 20 mL) will be obtained at baseline, at the time of prostatectomy and at a follow-up visit 4 weeks following the procedure for correlative studies to examine levels of pSTAT3 in PMBCs and selected angiogenic markers. A total of 10 mL will be collected in a CPT tube (for PBMC isolation), and a separate aliquot of 10 mL will be collected in an EDTA tube (for assessment of angiogenic markers) at

the specified times of collection. Blood will be delivered to the lab of [name] (Beckman Research Institute, Room 3220) within four hours of collection.

For isolation of PBMCs, 10ml of the whole blood in the CPT tube will be sent to the laboratory of [name] (in the Beckman Research Institute Building, Room 3111) within 4 hours of collection to avoid degradation of the phosphomoieties (i.e., pSTAT3) assessed in this protocol. If a sample is not delivered to the laboratory within a 4 hour time frame, the sample will be discarded. CPT tubes will be centrifuged at 1800 x g (approximately 2800 rpm on a Sorvall RT6000 centrifuge) for 20 minutes at room temperature. After centrifugation, plasma in the CPT tubes will be gently pipetted against the gel plug to dislodge cells stuck to the top of the gel. The cell suspension will be transferred to a 50 mL conical polypropylene tube. cRPMI will be added to a total of 40 mL. A 10 μ L aliquot of cell suspension for counting will be removed. The 50 mL tubes will then be centrifuged at 250 x g for seven minutes at room temperature. When centrifugation is complete, the supernatant will be aspirated. PMBCs will be either cryopreserved or used fresh.

Analysis of pSTAT3 in PBMCs will be conducted through previously reported techniques (Chalmin F, Ladoire S, Mignot G, et al. Membrane-associated Hsp72 from tumor-derived exosomes mediates STAT3-dependent immunosuppressive function of mouse and human myeloid-derived suppressor cells. *J Clin Invest* 2010;120:457-71.). PBMCs will be immersed in a mixture of PBS, 2% FCS and 0.1% (wt/vol) sodium azide with Fc III/IIR-specific antibody to block nonspecific binding and stained the cells with different combinations of fluorochrome-coupled antibodies to CD11c, I-Ab (MHC class II), CD86, CD11b, Gr1, CD49b, CD3, CD25 or Lag-3, or with annexin V (BD Biosciences). We collected fluorescence data on FACSCalibur (Beckton Dickinson) and analyzed them using FlowJo software (Tree Star). This method has been previously published by Chalmin et al.

For assessment of angiogenic markers, 10 mL of blood will be centrifuged (1500 rpm for 5 minutes) to separate plasma. Plasma concentration of VEGF-A, PDGF-AB and soluble VEGFR-2 were determined by enzyme-linked immunosorbent assay (ELISA) according to manufacturer's instructions from appropriate kits to quantitate these entities (R & D Systems). These methods have been previously reported by Kontovinis et al (Kontovinis L, Papazisis K, Touplikioti P, Andreadis C, Mouratidou D, Kortsaris A. Sunitinib treatment for patients with clear-cell metastatic renal cell carcinoma: clinical outcomes and plasma angiogenesis markers. *BMC Cancer* 2009;9:82.)

10.2 Study calendar for patients randomized to observation

	Pre-Study	Wk 1	Wk 5	Wk 9	Wk 21	Wk 33	Wk 45	Wk 57	Wk 69	Off Study
Axitinib 5 mg oral bid ^a										
Prostatectomy/PLND				X						
Informed Consent		X								
Demographics		X								
Medical history		X								
Concurrent meds		X								
Physical exam ^e	X		X	X	X	X	X	X	X	X
Vital signs	X		X	X	X	X	X	X	X	X
Height	X									
Weight	X		X	X	X	X	X	X	X	X
Performance Status	X		X	X	X	X	X	X	X	X
CBC w/diff, plts*	X		X	X	X	X	X	X	X	X
Serum chemistry ^{b*}	X		X	X	X	X	X	X	X	X
Lipid panel (with LDL)*	X									
Thyroid function tests (TSH, fT4)*	X									
PT, PTT, INR*	X									
PSA*	X		X	X	X	X	X	X	X	X
Correlative blood (Section 9.1)	X		X	X						
Adverse event evaluation									X	
Bone scan (section 4.1.1)	X									
CT/MRI(section 4.1.1)	X									
UA ^{f*}	X									X
Collection of tumor specimens (Section 9.1)				X						

a: Excepting adjustments for toxicity. b: Albumin, alkaline phosphatase, total bilirubin (direct bilirubin should be obtained level is $>1.5 \times$ ULN), bicarbonate, BUN, calcium, chloride, creatinine, glucose, LDH, phosphorus, potassium, total protein, SGPT[ALT], GGT, sodium. c: After week 81, on study, continue assessments noted at weeks 9, 21, and 33 every 12 weeks biochemical recurrence. d: Off-study evaluation. e: Patients will be supplied with a blood pressure cuff. At the specified in 2 and week 4 of axitinib therapy), the study nurse will call the patients to obtain blood pressure data and report any abnormal to the treating clinician. The treating clinician will dictate a progress note incorporating these data using the template in Appendix 2. If proteinuria is $\geq 2+$ for protein then a 24-hour urine collection can be done and the patient may enter only if urinary protein is <2 g per 24 hours. f: Clinic visits and laboratories prior to week 9 may be performed/collected within ± 3 days of the dates specified in the study calendar. From week 9 onwards, all clinic visits and laboratories may be performed/collected within ± 7 days of the dates specified in the study calendar. Pre-study labs may coincide with day 1 labs if performed within ± 3 days.

11.0 Evaluation Criteria/Measurement of Effect

11.1 Assessment of the pre-metastatic niche

Normal lymph node tissue will be assessed for pre-metastatic niche density, characterized as the average number of VEGFR1-positive clusters in 8 distinct 40x microscopic fields. This assessment will be performed through previously defined techniques.

11.2 Time to Biochemical Recurrence

Time to biochemical recurrence will be defined as the number of days elapsed between prostatectomy and the first recording of a PSA value ≥ 0.2 .

11.3 Time to Metastatic Recurrence

Time to metastatic recurrence will be defined as the number of days elapsed between prostatectomy and the first bone scan or CT scan with findings consistent with metastatic prostate cancer.

11.4 Overall survival

Overall survival will be defined as the number of days elapsed between prostatectomy and date of death.

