4.1.2.7 ECOG PS

- 4.1.2.8 Clinical laboratory assessments, as listed on the study calendar.
- 4.1.2.9 Verification of an operative date for prostatectomy/pelvic lymph node dissection that allows for the 28 day therapeutic period as well as a 48 hour washout period prior to surgery. Prostatectomy may be performed via any accepted methodology (open, laparoscopic, robotic-assisted, etc.). Notably, standard wait times for prostatectomy at City of Hope vary between 5-6 weeks from the time of biopsy confirmation of prostate cancer. Thus, it is not anticipated that the current protocol will delay standard of care therapies on the control or experimental arms.
- 4.1.2.10 Randomization to either surgery alone or preoperative axitinib therapy, to be performed by the designated study biostatistician

4.1.3 Pre-dose Assessments on Day 1 for patients randomized to axitinib (Note: Day 1 for patients randomized to axitinib treatment is considered the first day of axitinib therapy, whereas Day 1 for patients randomized to observation will represent the date of surgical intervention. Thus, the observation period reflects the time elapsed between the date of consent and the date of surgery.)

- 4.1.3.1 Physical examination: to identify any changes in the subject's mental and medical conditions since baseline assessment that would make him/her ineligible for the study.
- 4.1.3.2 Blood pressure measurements: subjects must have a blood pressure reading of <140/90mmHg to be eligible. If anti-hypertensives were initiated and/or dosing has been adjusted during the Baseline Period, the blood pressure must be reassessed on two occasions consecutively that are separated by a minimum of 1 hour. The mean SBP/DBP values from both blood pressure assessments must be <140/90mmHg in order for a subject to be eligible. These two assessments must also be the most recent ones prior to treatment (the blood pressure values from the later assessment will be used as the subject's baseline blood pressure values).
- 4.1.3.3 ECOG PS.
- 4.1.3.4 Record all the medication(s) received within 2 weeks prior to the first dose of study medication and indicate if the medication is continuing.
- 4.1.3.5 Obtain archived tumor tissue samples for biomarker assessments.

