6.1.1 Schedule

In patients on the experimental arm, axitinib should be taken at a dose of 5 mg oral bid, with 28 days of therapy constituting 1 cycle.

The date of initiation of axitinib therapy will be contingent upon the date selected for prostatectomy and pelvic lymph node dissection, with 28 days of planned therapy to conclude 48 hours prior to surgical intervention.

In patients on the control arm, no systemic therapy will be instituted. Rather, prostatectomy and pelvic lymph node dissection will be carried out within 5-6 weeks after biopsy confirmation of prostate cancer.

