14.0 Statistical Considerations

14.1 Study Design

14.1.1 The study is an open label, randomized phase II assessment of axitinib as pre-surgical therapy in high risk prostate cancer. In particular, a permuted block randomization scheme will be carried out to achieve treatment/control balance. To avoid selection bias, the blocking scheme will be masked to the principal investigator. The number of blocks will be determined by stratifying high risk patients according to PSA levels (≥ 20 or not) and Gleason scores (≥ 8 or not). For each block, we will randomly choose one arrangement from all possible realizations.*Primary Endpoints*: The primary endpoint of this study is pre-metastatic niche density, as defined by the average number of VEGFR1 clusters in 8 distinct 40x microscopic fields. We will use a two sample student's T-test to compare the primary endpoint of pre-metastatic niche density in the regional lymph nodes of patients treated with axitinib, as compared to the pre-metastatic niche density in the lymph nodes of patients enrolled on the control arm. With a sample of 22 patients per group, we will have 80% power to determine significance across groups if the average niche density is 3.13 in patients in the control arm, and at most 2.19 in patients treated with axitinib, with a common standard deviation 1.43 using a one-sided t-test assuming a type I error = 10% (Calculated using nQuery Advisor 6.01) Taking this into consideration, 30 patients per group will be recruited according to an empirical replacement rate of 27%. The intention-to-treat analysis will be the primary analysis conducted to obtain unbiased comparisons between the treatment and control. In addition, some as-treated subgroup analysis would also be investigated if necessary.*Secondary Endpoints*: Toxicity, time to biochemical recurrence, time to metastatic recurrence. With respect to secondary endpoints, Cox regression will be used (with the log-rank test) to compare time to biochemical recurrence (PSA ≥ 0.2), TTP and OS in patients treated with axitinib to patients treated with surgery alone. The Chi-square test will be used to compare the pStat3, LOX expression and MDSC density in patients treated with axitinib to patients treated with surgery alone. Descriptive statistics will be used to compare serum levels of VEGF-A, sVEGFR2, PDGF-AB and pSTAT3 at various timepoints during therapy.

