14.1.2 *Stopping Rules.* Toxicity will be monitored on an ongoing basis. If the number of unacceptable toxicities exceeds 1 in the first 3 patients, or exceeds 2 in the first 6 patients or more than 25% thereafter, the study will hold accrual for an amendment regarding treatment modifications or study termination. Toxicity will be graded and recorded for each patient in this population according to CTCAE 4.0. Also, a delay in surgery exceeding 7 days as a consequence of axitinib-related toxicity will be considered an unacceptable toxicity.

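### Overall survival and time to metastatic recurrence start at prostatectomy, so a randomised man who never reaches surgery cannot enter the between-arm comparison

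*Combined protocol and SAP*

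**What the plan says.** **Time origin.** Section 11.4: "Overall survival will be defined as the number of days elapsed between prostatectomy and date of death". Section 11.3: "Time to metastatic recurrence will be defined as the number of days elapsed between prostatectomy and the first bone scan or CT scan". Section 11.2 has the same origin: "Time to biochemical recurrence will be defined as the number of days elapsed between prostatectomy and the first recording of a PSA value".

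**Order of events.** Item 4.1.2.10, among the screening assessments, places the allocation: "Randomization to either surgery alone or preoperative axitinib therapy, to be performed by the designated study biostatistician". Section 6.1.1 then schedules axitinib back from the operative date, "with 28 days of planned therapy to conclude 48 hours prior to surgical intervention".

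**Comparison.** Section 14.1.1 uses Cox regression with the log-rank test to compare time to biochemical recurrence, "TTP and OS in patients treated with axitinib to patients treated with surgery alone". TTP is not defined in Section 11; I take it to be time to metastatic recurrence.

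**Analysis principle.** Section 14.1.1 also says: "The intention-to-treat analysis will be the primary analysis conducted to obtain unbiased comparisons between the treatment and control". That sentence stands in the primary-endpoint text, before the secondary endpoints begin.

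**Influence of treatment on surgery.** The stopping rules in Section 14.1.2 count as unacceptable toxicity "a delay in surgery exceeding 7 days as a consequence of axitinib-related toxicity".

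I found no start date, censoring rule or other handling for a randomised man who has no prostatectomy.

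**The concern.** An analysis of randomised arms keeps the protection of randomisation only if entry does not depend on something that happens afterwards. Here entry depends on having had surgery. Without a prostatectomy date the interval in Sections 11.3 and 11.4 cannot be calculated, so the man is excluded by construction, and any death or metastasis before surgery goes uncounted in these endpoints. The drug is given in one arm only, in exactly the window between randomisation and time zero, so the exclusions may differ between arms in number and in kind.

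The plan's own follow-up shows the gap. Sections 7.0 and 7.1 keep men taken off axitinib for intolerable toxicity under follow-up for survival, with no condition that they had surgery. A death can therefore be recorded that the survival definition has no way to use.

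At stake is the validity of two secondary comparisons. The synopsis names both outcomes among the hoped-for clinical benefits, and metastatic recurrence is a listed secondary objective.

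**Working it through.** **1. Plan's own figures.** The documents give no event count, hazard ratio or power for either endpoint, so there is nothing to reproduce for them. The one stated power is for niche density (Section 14.1.1): difference 3.13 − 2.19 = 0.94, standard deviation 1.43, 22 per arm, one-sided 10%. The noncentral t calculation gives 81.0%, which agrees with the stated 80%. It does not depend on the survival time origin.

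**2. Gap between randomisation and time zero, axitinib arm.** Section 6.1.1: 28 days + 48 hours = 30 days from first dose to surgery. Randomisation comes before the first dose, so the gap is about 30 days or more. In the control arm, surgery falls 5-6 weeks after biopsy confirmation. The gap from randomisation is not stated.

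**3. Who has a time zero under Sections 11.3 and 11.4.**

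| Randomised man | Prostatectomy date? | Enters the comparison? |
|---|---|---|
| Has surgery on schedule | yes | yes |
| Stops axitinib for toxicity, still has surgery | yes | yes |
| Surgery delayed by toxicity | yes, later | yes, with a later start |
| Dies before surgery | no | no |
| Develops metastases and has no surgery | no | no |
| Cancels surgery | no | no |

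**4. Weight of one man.** With 30 per arm (Section 14.1.1), 1/30 = 3.3%.

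**5. Possible size of the bias (assumptions, not document figures).** Suppose there is no drug effect. In each arm a fraction q of men has k times the hazard of the rest. In the axitinib arm these men miss surgery and are excluded; in the control arm they are operated on and counted. Early in follow-up:

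apparent hazard ratio = 1 / [(1 − q) + q·k]

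| q | Men of 30 | k = 1 | k = 2 | k = 3 |
|---|---|---|---|---|
| 0.03 | 0.9 | 1.00 | 1/1.03 = 0.97 | 1/1.06 = 0.94 |
| 0.10 | 3 | 1.00 | 1/1.10 = 0.91 | 1/1.20 = 0.83 |
| 0.20 | 6 | 1.00 | 1/1.20 = 0.83 | 1/1.40 = 0.71 |

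The true ratio is 1.00 throughout. If the men lost have the same hazard as the rest (k = 1), nothing is distorted. If theirs is lower, the distortion runs against axitinib. If both arms lose the same kind of men in the same proportion, it cancels.

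**The case against.** The case on the other side is substantial, and most of it limits the point without removing it.

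- **Intention-to-treat.** A reader might infer that the plan labels the survival comparison intention-to-treat and then contradicts itself. It does not say so outright: the sentence belongs to the primary-endpoint text, and the Cox sentence speaks of patients treated. This stands. If the principle does not reach these endpoints, however, the plan names no population for them, and the exclusion remains.
- **The 27%.** A reader might take the 27% replacement rate as the share of men without surgery (about 8 of 30). Section 6.5 ties replacement to receiving less than 75% of planned axitinib. Nothing says that such a man forgoes prostatectomy, and if he is operated on he has a time zero. The 27% must not be used as a non-surgery rate.
- **Toxicity.** A reader might assume that stopping axitinib for toxicity means no surgery. Section 6.5 lists reasons to stop treatment, not to cancel the operation.
- **Direction.** It is tempting to say that the axitinib arm will look better than it is. That requires the men lost to be at higher risk and the losses to be concentrated in that arm. Control men can cancel too: Section 3.1.11 provides for a radiation oncology consultation in both arms.
- **Size.** Known metastatic disease is excluded at entry, and the calendars schedule imaging only before study, so few metastases would be found between randomisation and surgery. A toxicity delay shifts the clock by little, because the operative date is verified at screening. Both stand.
- **Safety.** Toxicity before surgery is captured by Section 14.1.2 and deaths on treatment by Section 13.4, so safety monitoring is not affected.
- **Weight.** The comparisons are secondary and unpowered, and survival is missing from the endpoint lists although Section 14.1.1 compares it.

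What survives is that a man without surgery has no survival or metastasis time, and the documents provide no rule for him.

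**Conclusion.** The point holds in a limited form. As defined in Sections 11.3 and 11.4, the two endpoints can be computed only for men who reach prostatectomy, an event after randomisation that axitinib may influence. The comparison in Section 14.1.1 is restricted accordingly, which departs from the intention-to-treat aim so far as that aim is meant to extend to these endpoints.

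The size cannot be read from the documents, because they give no non-surgery rate. What is certain is the 3.3% weight of each man. Under the stated assumptions (loss of 3% to 20% in the axitinib arm only, hazard 2 to 3 times that of the rest, no drug effect) the apparent early hazard ratio would lie between 0.97 and 0.71. It stays at 1.00 if the hazard is equal. The bias is possible, not established.

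The primary endpoint's power and the sample size do not change. A surgical origin has a natural reason for biochemical recurrence, since its PSA threshold of 0.2 is a post-surgical one. The correction should be made because it is nearly free, not because the damage is known to be large.

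**What to change.** **Sections 11.3 and 11.4.** Define overall survival and time to metastatic recurrence from the date of randomisation, in all randomised men, by assigned arm, whether or not surgery took place. Censor event-free men at last follow-up for survival and at last disease assessment for metastasis. Since the calendars schedule imaging only before study, say which assessment sets that censoring date. Sections 4.1 and 5.1 let a randomised man be classed as a screen failure or have his registration cancelled, so the definition should state how such men are handled.

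**Section 14.1.1.** Name this population for the Cox and log-rank comparison, and use the same endpoint name as Section 11.3 in place of TTP if that is what is meant. Keep the surgery-anchored analysis as a labelled supportive one.

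**Section 11.2.** Leave time to biochemical recurrence anchored at surgery, and report the number of randomised men without surgery, by arm, beside it. Moving its clock to randomisation while counting PSA events only after surgery would keep unoperated men at risk but unable to have an event, which could preserve the same bias.

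**Cost.** Wording only, a free improvement. Randomisation is central (Section 5.1), so the dates are held. Sample size, visits and treatment do not change.

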11.5 Erectile Dysfunction

Erectile dysfunction will be defined by CTCAE 4.0, and we will assess the rate of grade ≥ 3 toxicity.

11.6 Urinary Incontinence

Urinary incontinence will be defined by CTCAE 4.0 criteria, and we will assess the rate of grade ≥ 3 toxicity.

12.0 Data Reporting/Protocol Deviations

12.1 Data Reporting

12.1.1 Confidentiality of Records

The original data collection forms will be stored at the originating institution in a secure location. When results of this study are reported in medical journals or at meetings, identification of those taking part will be withheld. Medical records of patients will be maintained in strictest confidence, according to current legal requirements. They will be made available for review, as required by the FDA or other authorized users such as the NCI, under the guidelines established by the Federal Privacy Act.

